### 3.6 Methods for ensuring blinding

The study is a double-blind study. AstraZeneca staff involved in the study, the patients, and the investigators/site staff involved in the treatment of the patients or in their clinical evaluation will not be aware of the treatment allocation.

Placebo solution will be visually matched with benralizumab solution. Both benralizumab and placebo will be provided in an accessorized pre-filled syringe.

As PK sample will be analysed only for patients receiving benralizumab, treatment data (randomization list and kit list) will be available to bioanalytical lab personnel for PK sample analysis during the conduct of study. The bioanalytical lab personnel, are independent of the study team and sites, will not engage in study activities other than PK/immunogenicity sample

analysis. The treatment data will only be sent to the lab scientist and will be restricted within the lab scientist and analysts. The information in the randomization and kit list will be kept from other personnel involved in the conduct of the study and any CRO handling data until study unblinding.

### **Maintaining the blinding to the patient's blood eosinophil counts**

While not entirely specific, patients on active benralizumab treatment are expected to have lower blood eosinophil counts than patients on placebo. Procedures to mitigate unblinding on this basis include:

- From Visit 4 on, eosinophil, basophil or monocyte count will be redacted from central laboratory reports to prevent the Principal Investigator/designee from possibly deducing the 'eosinophil + basophil' contribution to the complete blood count. In cases where the Investigator requires an eosinophil, basophil or monocyte count for managing safety issues, AstraZeneca physician should be notified of all such cases, without being revealed the eosinophil, basophil or monocyte count.
- Regarding lab results obtained during the treatment period but ordered outside of the clinical trial, centre staff who are directly involved in the patient's treatment and evaluation should remain blinded to any eosinophil, basophil and monocyte results included as part of outside lab reports.
- If the Investigator have to order any local safety laboratory assessments to follow up patient's safety, the requested tests should be restricted to the question at hand. For example, if a haemoglobin is desired the Investigator should avoid ordering a complete blood cell count with differential.

## **3.7 Methods for unblinding**

Individual treatment codes, indicating the treatment randomisation for each randomised patient, will be available to the Investigator(s) or delegate at the study centre from the IWRS/IVRS. Further detail on how to unblind a patient's treatment allocation will be described in the IWRS/IVRS user manual provided to each study centre.

The treatment code should not be broken except in medical emergencies when the appropriate management of the patient requires knowledge of the treatment randomisation. The Investigator should document and report the action to AstraZeneca, without revealing the treatment given to patient to the AstraZeneca staff.

AstraZeneca retains the right to break the code for serious adverse events (SAEs) that are unexpected and are suspected to be causally related to an IP and that potentially require expedited reporting to regulatory authorities. Treatment codes will not be broken for the planned analyses of data until all decisions on the evaluability of the data from each individual patient have been made and documented.

### **3.8 Restrictions**

#### **3.8.1 Asthma medication restrictions**

##### **(a) Use of short-acting $\beta_2$ agonists (SABA)**

Regularly scheduled SABA use in the absence of any asthma symptoms and/or planned exercise is discouraged from enrolment and throughout the study duration.

Prophylactic use of SABA in the absence of symptoms (e.g., prior to planned exercise) is discouraged. However, if deemed necessary by the patient and Investigator, it can be used, but prophylactic inhalations should not be recorded in the Asthma Daily Diary, such use should be documented in medical notes and recorded in the Electronic Case Report Form (eCRF).

SABA via a metered dose device is permitted as needed for worsening asthma symptoms (ie, rescue use) and will be recorded in the Asthma Daily Diary as number of inhalations.

Rescue use of SABA administered via jet or ultrasonic nebulisation is allowed. Occasions where SABA was administered via nebulisation will be recorded separately from metered dose inhaler (MDI) inhalations in the Asthma Daily Diary.

**(b) Use of short acting anticholinergics** (e.g., ipratropium) as a rescue treatment for worsening asthma symptoms outside of managing an asthma exacerbation event is not allowed from enrolment and throughout the study duration

**(c) Use of long-acting beta-agonists as a reliever** (e.g., Symbicort Maintenance and Reliever Treatment) is not allowed from enrolment and throughout the study duration

##### **(d) Maintenance of asthma controller medications**

The patient's usual pre-study ICS-LABA formulation, dose and regimen, and any other additional allowed asthma controllers that they may have been taking prior to enrolment, should be continued unchanged from visit 1 until the end of study.

Additional maintenance asthma controller medications (e.g., tiotropium, LTRAs, cromone, theophylline, and oral corticosteroid), that are locally approved in a country for the treatment of asthma and that have been used for at least 30 days prior to Visit 1 are allowed.

**Changes to the patient's background controller regimen are discouraged during the treatment period**, unless judged medically necessary by the Investigator. All changes in the patient's background medication should be discussed beforehand with the AstraZeneca study physician and documented in source along with rationale for change and recorded in eCRF.

Asthma exacerbations should be treated with oral or other systemic corticosteroids according to standard practice.

**(e) Asthma medication restrictions on the days of scheduled spirometry visit**

Pre- and/or post-dose spirometry assessments will be performed at the study centre at scheduled visits (see [Table 1](#) and [Table 2](#)). Restrictions to patient's background medication are required prior to the spirometry as described below (also see [Section 5.1.2](#)):

**Screening Visit 2:** Patients should withhold their usual ICS, LABA, Long-acting anti-muscarinic (LAMA), LTRA or theophylline medications on the morning of the FEV1 measurement and reversibility test. Twice daily ICS- LABA therapies should be withheld for 12- 24 hours; once daily therapies containing ICS, LABA, LAMA, LTRA, theophylline therapies should be withheld for  $\geq 24$  hours for eligibility assessment (see [Section 3.1](#), inclusion criterion 7).

In case the patient does not meet the reversibility eligibility criteria, and a second re-test is done (not earlier than next calendar day and not later than 7 calendar days after the failed attempt), asthma medication restrictions described above should be applied. In addition, SABA should not be used within 6 hours of these spirometry assessments. The patient's usual asthma medications may be administered following completion of the screening lung function procedures.

**Treatment Visits 4-17:** Patients should withhold their usual ICS, LABA, LAMA, LTRA or theophylline medications on the morning of the scheduled spirometry. Twice daily ICS- LABA therapies should be withheld for 12- 24 hours; once daily therapies containing ICS, LABA, LAMA, LTRA or theophylline therapies should be withheld for  $\geq 24$  hours prior to the spirometry assessment. This is especially important prior to scheduled spirometry assessments (see [Table 2](#)) in order to maintain the integrity of planned efficacy analyses around lung function improvement. In addition, SABA should not be used within 6 hours prior to the spirometry assessments. The patient's usual asthma controller medications may be administered following completion of the pre-BD spirometry. The suggested order of administration of the patient's usual asthma controller and IP administration relative to scheduled pre -BD spirometry is given in [Section 5.1.2](#).

If the patient has taken their usual ICS, LABA, LAMA, LTRA or theophylline asthma controller medication on the morning of the scheduled spirometry visit, the Investigator/authorized delegate should remind the patient of the importance of withholding their usual morning asthma medication, and reschedule the visit for another day, within the allowed window.

If the patient has taken rescue SABA within 6 hours of the planned centre visit spirometry they should:

- 1 Remain at the centre until such time that the 6 hour withholding time has been reached if it does not exceed the 1.5 hour spirometry window, or
- 2 Return on another day, within the visit window.

**(f) Asthma medication restrictions prior to home peak expiratory flow testing**

Patients should avoid taking their morning asthma controllers prior to the morning home Peak Expiratory Flow (PEF) testing, and should conduct the evening home PEF testing before taking evening asthma controllers. When possible, home PEF testing, should be taken at least 6 hours after the last dose of SABA rescue medication.

**(g) Asthma medication restrictions on unscheduled visits**

Asthma medication restrictions on unscheduled visits may not be feasible, and may be applied at the discretion of the Investigator. Timing of recent controller and rescue SABA use relative to the unscheduled spirometry should be noted in the record

**(h) Asthma medication restrictions at centre visits with scheduled ECG assessment**

The patients should be instructed not to take their usual asthma controller medication (ie, LABA) prior to scheduled ECG assessment. Use of SABA should be avoided within 6 hours before ECG assessments. The medication restriction is waived for the screening ECG and Visit 1.

**3.8.2 Other medication restrictions**

- (a) Use of immunosuppressive medication (other than prior, stable oral corticosteroid for the maintenance treatment of asthma) is not allowed. Topical administration of immunosuppressive medication may be allowed at the discretion of the Investigator after discussion with the AstraZeneca study physician. Please see Section 3.2 exclusion criterion 14 for examples and further details.
- (b) Receipt of live attenuated vaccines within 30 days prior to randomisation, during the treatment period, and for 12 weeks after the last dose of the IP is not allowed.
- (c) Patient should not receive allergen immunotherapy injection on the same day as the IP administration.
- (d) Patients should not take any other excluded medications:  
  
Five-lipoxygenase inhibitors (e.g., Zileuton)  
  
Roflumilast

Oral or ophthalmic non-selective  $\beta$ -adrenergic antagonist (eg, propranolol).

A table with medication-related restrictions is presented in the [Appendix F](#).

### **3.8.3 Other restrictions**

- (a) Fertile and sexually active female patients should use effective contraceptive methods throughout the study and at least for 12 weeks after last administration of the IP. (see Section 3.1, inclusion criterion 3 and Section 6.6).
- (b) Patients must abstain from donating blood, plasma from the time of informed consent, and assent when applicable, and for 12 weeks after last dose of IP.

## **3.9 Discontinuation of investigational product**

Patients may be discontinued from investigational product (IP) in the following situations:

- 1 Patient decision. Patients are free to discontinue treatment at any time, without prejudice to further treatment (see Section 3.10).
- 2 Adverse event (AE) that, in the opinion of the Investigator or AstraZeneca, contraindicates further dosing.
- 3 Risk to patient as judged by the Investigator or AstraZeneca.
- 4 Severe non-compliance to study protocol.
- 5 Eligibility requirement found not to be fulfilled (see section 3.4).
- 6 Pregnancy.
- 7 Lost to follow-up.
- 8 Development of any study specific criteria for discontinuation:
  - Anaphylactic reaction to the IP requiring administration of epinephrine.
  - Development of helminth parasitic infestations requiring hospitalization.
  - An asthma-related event requiring mechanical ventilation.

If a patient misses more than 2 doses of IP at any time within a calendar year, it is strongly recommended that a conversation between the investigator and AZ study physician takes place to review the patient's adherence to treatment and decide on further patient's disposition.

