### 1.3 Benefit/risk and ethical assessment

There are few treatment options for patients whose asthma remains uncontrolled on medium to high-dose ICS-LABA (GINA 2014). The evidence base for oral add-on therapies (ie, oral corticosteroids, leukotriene inhibitors, and xanthenes) is extremely limited. Anti-IgE therapy (ie, omalizumab) may improve control in patients with severe asthma and IgE-mediated allergy to a perennial allergen. Tiotropium is a long-acting bronchodilator that has recently been shown to produce improvement in lung function and exacerbation risk (pooled data) in patients with severe asthma, with inconsistent effects on other measures of asthma control (Kerstjens et al 2012). As such, new therapies are needed for asthma management in patients who remain uncontrolled on standard of care.

In adult patients whose asthma was poorly controlled on medium-to-high dose ICS-LABA benralizumab, at fixed doses of  $\geq 20$  mg, produced improvements in multiple metrics of asthma control including the annual rate of asthma exacerbations, lung function, ACQ-6 scores, and symptoms (Castro et al 2014). These findings have subsequently been confirmed in two large Phase 3 studies (Bleecker et al 2016, FitzGerald et al) where a fixed dose of 30 mg was given either every 4 weeks or every 8 weeks. Clinical benefit appeared to be greatest in patients with blood eosinophil counts  $\geq 300/\mu\text{L}$ . The blood eosinophil count below which

benralizumab is generally not effective remains unclear at this point in time, and will be explored in this study.

Development of anti-drug antibodies (ADA) to benralizumab has been documented. Theoretical risks of developing ADA include decreased drug efficacy and hypersensitivity reactions (e.g., anaphylaxis or immune complex disease). There was no apparent impact of ADA on overall benralizumab safety or efficacy in the previous Phase 3 studies in asthma. Serious hypersensitivity reactions (including anaphylaxis) are an identified risk of biologic therapy, including benralizumab. Anaphylaxis may be life-threatening. Risk minimization includes observation in line with clinical practice at the clinical site following IP administration for the appearance of any acute drug reactions.

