### **3.2 Exclusion criteria**

Patients should not enter the study if any of the following exclusion criteria are fulfilled:

- 1 Known history of clinically important pulmonary disease other than asthma (e.g., active lung infection, Chronic obstructive pulmonary disease (COPD), bronchiectasis, pulmonary fibrosis, cystic fibrosis, hypoventilation syndrome associated with obesity, lung cancer, alpha 1 anti-trypsin deficiency, and primary ciliary dyskinesia) or ever been diagnosed with pulmonary or systemic disease, other than asthma, that are associated with elevated peripheral eosinophil counts (e.g., allergic bronchopulmonary aspergillosis/mycosis, Churg-Strauss syndrome, hypereosinophilic syndrome).
- 2 Known history of any disorder, including, but not limited to, cardiovascular, gastrointestinal, hepatic, renal, neurological, musculoskeletal, infectious, endocrine, metabolic, haematological, psychiatric, or major physical impairment that is not stable in the opinion of the Investigator and could:
  - Affect the safety of the patient throughout the study
  - Influence the findings of the studies or their interpretations
  - Impede the patient's ability to complete the entire duration of study.
- 3 Known history of allergy or reaction to the investigational product (IP) formulation.

- 4 Known history of anaphylaxis to any biologic therapy.
- 5 A helminth parasitic infection diagnosed within 24 weeks prior to the date informed consent, and assent when applicable, is obtained that has not been treated with, or has failed to respond to standard of care therapy.
- 6 Acute upper or lower respiratory infections requiring antibiotics or antiviral medication within 30 days prior to the date informed consent, and assent when applicable, is obtained or during the screening period.
- 7 Any clinically significant abnormal findings in physical examination, vital signs, haematology, clinical chemistry, or urinalysis during screening period, which in the opinion of the Investigator, may put the patient at risk because of his/her participation in the study, or may influence the results of the study, or the patient's ability to complete entire duration of the study.

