## 6.4 Reporting of serious adverse events

All SAEs have to be reported, whether or not considered causally related to the IP, or to the study procedure(s). All SAEs will be recorded in the CRF.

If any SAE occurs in the course of the study, then investigators or other centre personnel will inform appropriate AstraZeneca representatives within 1 day, ie, immediately but **no later than 24 hours** from when he or she becomes aware of it.

The designated AstraZeneca representative will work with the Investigator to ensure that all the necessary information is provided to the AstraZeneca Patient Safety data entry site **within 1 calendar day** of initial receipt for fatal and life threatening events **and within 5 calendar days** of initial receipt for all other SAEs.

For fatal or life-threatening AEs where important or relevant information is missing, active follow-up will be undertaken immediately. Investigators or other centre personnel will inform AstraZeneca representatives of any follow-up information on a previously reported SAE within 1 calendar day, i.e., immediately but **no later than 24 h** from when he or she becomes aware of it.

Once the investigators or other centre personnel indicate an AE is serious in the Web-based Data Capture (WBDC) system, an automated email alert will be sent to the designated AstraZeneca representative.

If the WBDC system is not available, then the Investigator or other study centre personnel is to report the SAE to the appropriate AstraZeneca representative by telephone.

The AstraZeneca representative will advise the Investigator/study centre personnel how to proceed.

The reference document for definition of expectedness/listedness is the IB for the AstraZeneca drug.

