## **7.7 Management of investigational product-related reactions**

Appropriate drugs, such as epinephrine, H1 and H2 antihistamines, and corticosteroids, as well as medical equipment to treat acute anaphylactic reactions must be immediately available. Study personnel must be trained to recognize and treat anaphylaxis ([Lieberman et al 2010](#)). Details on anaphylaxis management are provided in [Appendix D](#).

Anaphylaxis will be defined as a serious reaction that is rapid in onset and may cause death ([Simpson et al 2006](#)). Anaphylaxis typically manifests as 1 of 3 clinical scenarios:

- 1 The acute onset of a reaction (minutes to hours) with involvement of the skin, mucosal tissue, or both, and at least 1 of the following: a) respiratory compromise; or b) reduced blood pressure or symptoms of end-organ dysfunction
- 2 Two or more of the following that occur rapidly after exposure: involvement of the skin/mucosal tissue, respiratory compromise, reduced blood pressure or associated symptoms, and/or persistent gastrointestinal symptoms
- 3 Reduced blood pressure after exposure

Patients will have had a pre-assessment (i.e., vital signs and lung function) prior to IP administration and should be observed after IP administration at the study site for the appearance of any acute drug reactions.

In order to help understand the potential drug-relatedness of any acute reaction, a blood sample should be drawn as close as possible to the event for additional ADA testing (if not already scheduled for this visit). Serum tryptase or other blood testing relevant to the diagnosis of anaphylaxis may be obtained at a local lab at the discretion of the Investigator.

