## A GUIDE TO INTERPRETING THE CAUSALITY QUESTION

When making an assessment of causality, consider the following factors when deciding if there is a “reasonable possibility” that an AE may have been caused by the drug.

- Time Course. Exposure to suspect drug. Has the patient actually received the suspect drug? Did the AE occur in a reasonable temporal relationship to the administration of the suspect drug?
- Consistency with known drug profile. Was the AE consistent with the previous knowledge of the suspect drug (pharmacology and toxicology) or drugs of the same pharmacological class? OR could the AE be anticipated from its pharmacological properties?
- De-challenge experience. Did the AE resolve or improve on stopping or reducing the dose of the suspect drug?
- No alternative cause. The AE cannot be reasonably explained by another aetiology such as the underlying disease, other drugs, other host or environmental factors.
- Re-challenge experience. Did the AE reoccur if the suspected drug was reintroduced after having been stopped? AstraZeneca would not normally recommend or support a re-challenge.
- Laboratory tests. A specific laboratory investigation (if performed) has confirmed the relationship?

In difficult cases, other factors could be considered such as:

- Is this a recognised feature of overdose of the drug?
- Is there a known mechanism?

Causality of ‘related’ is made if following a review of the relevant data, there is evidence for a ‘reasonable possibility’ of a causal relationship for the individual case. The expression ‘reasonable possibility’ of a causal relationship is meant to convey, in general, that there are facts (evidence) or arguments to suggest a causal relationship.

The causality assessment is performed based on the available data including enough information to make an informed judgment. With limited or insufficient information in the case, it is likely that the event(s) will be assessed as ‘not related’.

Causal relationship in cases where the disease under study has deteriorated due to lack of effect should be classified as no reasonable possibility.

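### Section 3.9 lists anaphylaxis to IP needing epinephrine only as a ground on which dosing may stop; no protocol text expressly forbids a further dose

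*Supplement*

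**What the plan says.** The list in Section 3.9 of the protocol opens with "Patients may be discontinued from investigational product (IP) in the following situations". Eight items follow. Items 2 and 3 cover an adverse event that speaks against further dosing and a risk to the patient; both rest on the view of the investigator or the sponsor. Item 8 covers study-specific discontinuation criteria, and its first entry is "Anaphylactic reaction to the IP requiring administration of epinephrine".

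At entry the protocol is strict. Exclusion criterion 3 in Section 3.2 is "Known history of allergy or reaction to the investigational product (IP) formulation" and criterion 4 is "Known history of anaphylaxis to any biologic therapy". Section 3 allows no exceptions to the entry criteria.

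Section 1.3 states the hazard: "Serious hypersensitivity reactions (including anaphylaxis) are an identified risk of biologic therapy, including benralizumab". It adds that anaphylaxis can threaten life.

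**The concern.** The permissive verb in the opening line of Section 3.9 governs every item below it, including the anaphylaxis entry. Read word for word, a patient who has had an anaphylactic reaction to the study drug, treated with epinephrine, falls under a criterion that allows dosing to stop but does not require it. The same history would have barred that patient from randomisation.

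At stake is the safety of a few patients. A repeat dose after anaphylaxis to the same product could be fatal, and the protocol leaves the decision to judgement for an event that it already names as a discontinuation criterion. Appendix G adds some weight: during a study disruption it lets a patient or caregiver give IP at home after the investigator has assessed suitability and training has been given. It does not exclude a patient with an earlier anaphylactic reaction to IP.

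**Working it through.** The protocol gives no figure on this point, so the check sets side by side every section that could govern the next dose.

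**Sections that might require a stop**

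- Section 3.4 has a mandatory stop, but only for patients randomised or started on treatment in error, and only where continuing is judged unsafe.
- Section 6.6.1 directs that IP be stopped at once in pregnancy. Pregnancy also stands in the Section 3.9 list, so the protocol does give a directive elsewhere for one listed item. Anaphylaxis has none.
- Section 7.4 holds back a dose for intercurrent illness or fever, and then reschedules it.
- Section 7.7 ("Anaphylaxis will be defined as a serious reaction that is rapid in onset and may cause death") and Appendix D cover definition, recognition, treatment and sampling. Neither mentions later doses.
- Section 3.11 refers to individual stopping criteria as a reason to halt the study, but sets no rule for a patient.
- Appendix A says "AstraZeneca would not normally recommend or support a re-challenge". This is a qualified remark in guidance on judging causality, not a dosing rule.
- Appendix G, on home dosing, adds no bar.

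None of these expressly ends dosing after anaphylaxis to IP.

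**Safeguards that do operate**

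- Under items 2 and 3 of Section 3.9, either the investigator or the sponsor can stop dosing.
- Section 6.4 requires that, for any serious adverse event, "then investigators or other centre personnel will inform appropriate AstraZeneca representatives within 1 day". Section 7.7 calls anaphylaxis serious, so a case needing epinephrine should be reported by this route.
- There is time to act. Doses fall at Weeks 0, 4, 8, 16, 24, 32 and 40. The nominal gap to the next dose is 4 × 7 = 28 days after dose 1 or 2, and 8 × 7 = 56 days after doses 3 to 6. With a report within 1 day, the sponsor knows about 28 − 1 = 27 or 56 − 1 = 55 days before the next dose, leaving visit windows aside.

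The text leaves a gap, and the surrounding procedures largely cover it.

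**The case against.** The strongest reply is that the opening line of Section 3.9 is a list of recognised grounds and does not grant discretion on each one. The same line covers loss to follow-up, where further dosing is impossible, and pregnancy, where Section 6.6.1 directs an immediate stop. Item 8 also omits the opinion wording of items 2 and 3 and labels its entries as criteria. If it were discretionary too, it would add nothing to those items. Repeated missed doses, by contrast, are sent to a recommended conversation with the study physician, and anaphylaxis is not given that softer route. Section 3.11 likewise suggests that binding individual criteria were intended.

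Much of this stands. A reader might infer from Section 3.9 that the protocol permits re-dosing after anaphylaxis. The documents do not support that: the layout of item 8 points towards a stop, Appendix A discourages re-challenge, and nothing endorses a further dose. The reply does not, however, supply a sentence that requires dosing to end. It shows what was probably meant, which is a reason to write it down.

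Two further objections are fair. A mandatory rule would still need someone to attribute the reaction to IP. And Section 7.4 requires administration in line with an IP Handling Instruction that is not among the documents; that Instruction or the Investigator's Brochure may already settle the matter.

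**Conclusion.** The point holds in a limited form. Version 5.0 does not expressly prohibit a further dose after on-study anaphylaxis to IP that needed epinephrine, although exclusion criteria 3 and 4 bar the same history at entry. Judgement under items 2 and 3, prompt reporting and the Appendix A remark make such a dose unlikely.

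The number of patients affected is expected to be very small, but it cannot be estimated because the documents give no rate of anaphylaxis or of re-dosing. One could count the scheduled doses still to come after a reaction, but that count would be the same for any event and does not measure harm.

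The conclusion rests on the protocol text alone and on reading the verb in Section 3.9 at face value. Severity is low. It is worth acting on because the risk is identified and potentially fatal, and the remedy costs almost nothing.

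**What to change.** Add one sentence to Section 3.9: IP must be permanently discontinued after an anaphylactic reaction to it that required epinephrine, and follow-up continues under Section 3.9.1. Refer to that sentence from Section 7.7 and Appendix D, so that staff handling a reaction see it. The other items of Section 3.9 need no change for this purpose.

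The cost is a wording amendment. A very small number of patients who might have tolerated more doses would stop IP. Section 3.9.1 encourages them to stay in the study, and Section 8.4.1.1 keeps data collected after discontinuation in the primary analysis, so the effect on the exacerbation comparison should be negligible.
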